### **4.3 Study Enrollment Procedures**

#### **4.3.1 Pre-screening:**

Local CA Patients: Patients under the care of the study principal investigator will be pre-screened for eligibility. Pre-screening will include a review of medical records, prior imaging, and laboratory studies. Depending on the date of the last clinically symptomatic hemorrhagic event, eligible patients will be contacted and briefed about the study and if interested, will be invited to the screening/baseline visit. Subjects will be sent a copy of the consent form for their review prior to their first study visit. We estimate that at least 50% of subjects will come from this source.

Referred CA patients: patients referred through the Angioma Alliance, other healthcare professionals, or self-referred will undergo pre-screening evaluation over the phone with the Trial Nurse (TN) or coordinator to determine eligibility for the trial. Patients meeting the pre-screening criteria will be sent a copy of the consent form and will be asked to send a digital copy of their most recent MRI scan to confirm their diagnosis. Once diagnosis is confirmed by the study PI, subjects will be invited for the screening/baseline research visit at the University of Chicago Medicine.

#### **4.3.2 Screening and Enrollment:**

All potential subjects will be scheduled to meet with the principal investigator. The visit will involve detailed screening, including collection of medical history, prior and concomitant medications, and a neurological examination to confirm eligibility. Surgical resection will be considered in every case as an alternative to medical therapy, per current standard of care. As part of the screening, blood tests will be performed, which in the case of successful enrollment, will serve as baseline laboratory results (Section 6.3.6). With verification of eligibility criteria, informed consent will be finalized. ***A travel stipend for each trial related visit will be provided to subjects from outside the Chicago area who are required to travel greater than 200 miles to the study center.***

#### **4.3.3 Baseline Imaging:**

Randomized subjects will undergo a baseline MRI, which will include special sequences utilized throughout the trial (DCEQP and QSM). This will be pre-scheduled at the same time as the screening visit (particularly for subjects traveling from outside the Chicago area), or as soon as practical for local patients.

## 5. STUDY INTERVENTION

### 5.1 Intervention, Administration, and Duration

Study drug will be administered orally as a single daily dose in the morning. Subjects in the treatment group will be started on their corresponding dose 80mg of atorvastatin or placebo. Should the subject report an adverse event meeting pre-specified criteria (Adverse events Category B below), he/she will be put on the lower dose (40 mg) of drug or matched colored placebo capsule.

Administration of study drug shall continue once daily dose in the morning for 24 total months with scheduled visits and repeat imaging at 12 and 24 months from enrollment, unless the subject reaches attrition or a safety endpoint before then. If new symptoms arise at any point after starting the study intervention subjects will be contacted by the study-designated TN for further assessment and be provided with instructions regarding continuation of study intervention based on the study adverse events management protocol (Section 7).

### 5.2 Handling of Study Intervention

A third party pharmacy will be contracted to formulate and supply atorvastatin and placebo capsules for the trial. The Research Pharmacy at the University of Chicago will be responsible for storage, packaging and dispensing the study drug in conjunction with the research team.

### 5.3 Concomitant Interventions

#### 5.3.1 Required Interventions

- Daily oral administration of the study drug.
- Laboratory blood testing at screening, 3, 12 and 24 months. Tests will include liver enzymes and creatinine kinase (to be repeated if clinically indicated).
- A total of three MRI scans involving special sequences for QSM and IV contrast material for DCEQP acquisition. IV contrast administration will be preceded by a blood test to check renal function as indicated per hospital policy.

#### 5.3.2 Prohibited Interventions

The following drugs are contraindicated throughout the trial as they are associated with increased risk of rhabdomyolysis when combined with statins. If clinically indicated the decision whether or not these medications can be taken should be discussed with the study PI who will weigh the risks and benefits of staying on study drug.

- Cyclosporine
- Fibrates
- Niacin
- Azol antifungals
- HIV/HCV protease inhibitors
- Macrolide antibiotics
- Colchicine

### 5.3.3 Precautionary Interventions

The following drugs interact with Atorvastatin. If unavoidable, extra measures should be put in place for closer monitoring.

- OCP
- Antacids
- Digoxin
- Lipid lowering resins
- Rifampicin
- Grapefruit juice
- Calcium channel blockers

 Values for norethindrone and ethinyl estradiol may be increased, co-administration of statins and an oral contraceptive increased serum levels for norethindrone and ethinyl estradiol. These increases should be considered when selecting an oral contraceptive for a woman taking atorvastatin.

Interfere with absorption of atorvastatin from GI tract

When multiple doses of atorvastatin and digoxin were co-administered, steady state plasma digoxin concentrations increased by approximately 20%. Patients taking digoxin should be monitored appropriately.

As well as other known activators of the Cyt-P450(3A4) isoform which metabolizes most statins in the liver. Interaction affects the pharmacokinetic properties of the drug leading to changes in serum concentration.

Contains one or more components that inhibit Cyt-P450(3a4) and can increase plasma concentrations of atorvastatin, especially with excessive grapefruit juice consumption (>1.2 liters per day).

Weak inhibitors of Cyt-p(3a4) system

### 5.4 Adherence Assessments

The team is in the process of evaluating potential electronic monitoring devices, an eDiary and a smart bottle. Both devices are equipped with a SIM card and programmed to wirelessly transmit compliance data to the study database in real time. Both devices are linked to a closed loop electronic feedback system that is programmed to set off reminders in escalating manner and ultimately notify the study team. In addition to compliance, these innovative monitoring systems will also allow subjects to notify the team early on of any adverse events or change in concomitant medications. All compliance data will be continuously recorded in the study database and will be used to guide decision-making. In addition, members of the research team in liaison with the local pharmacy will perform pill counts to confirm adherence at the time of follow up visits.

In addition, the TN or research coordinagtor shall contact each subject for scheduled phone calls every three months (to be completed every 10-14 weeks), with a structured questionnaire about compliance and tolerance.

## 6. CLINICAL, LABORATORY AND IMAGING EVALUATIONS

All enrolled subjects will go through the same schedule of investigations and follow up visits throughout the study period (Table 1).

### 6.1 Schedule of evaluations

Evaluation	V1 Screening (0)	V2 Safety labs, Phone call (3m)	V3,4 Phone call (6, 9m)	V5 Follow up (12m)	V6-8 Phone call (15,18,21 m)	V9 End of Study (24m)
Informed consent	X					
Demographics	X					
Inclusion/Exclusion criteria	X					
CCM History	X					
Statin History	X					
Medical/Surgical History	X			X		X
Prior and concomitant medications	X	X	X	X	X	X
Physical and Neurological Examination	X			X		X
MMSE	X			X		X
mRS	X	X	X	X	X	X
Euro-QoL-5D Scale	X			X		X
Euro-QoL VAS	X			X		X
Neuro-QoL	X			X		X
Intervention adherence/ Adverse Events*		X	X	X	X	X
MRI	X			X		X
Laboratory investigations						
• CBC	X					
• Renal functions	X	X		X		X
• LFTs	X	X		X		
• TFTs	X					
• CK	X	X		X		
• Lipid profile	X			X		X
• Hepatitis viral profile	X					
• HIV	X					
• Pregnancy test	X					
Study intervention initiation/continuation assessment	X	X	X	X	X	
Randomization	X					

*Table 1: AT CASH EPOC trial, schedule of evaluations.*

\*These are assessed at each follow-up, by automated weekly follow-up messages circulated by the electronic monitoring system, and in scheduled calls with each enrolled subject every three months (1-0-14 weeks), as described in section 5.4

## 6.2 Timing of Evaluations

### **6.2.1 Initial screening visit (V0) – up to 30 days prior to enrollment**

This visit may occur on the same day as the baseline visit (V2) at the discretion of the investigator. Subjects will undergo the following assessments and sign an informed consent form in order to be randomized into this study:

- Informed consent
- Obtain subject demographics
- Eligibility criteria (inclusion/exclusion criteria)
- Neurosurgical review (confirmation of diagnosis, date of last symptomatic hemorrhage, statin use, past medical and surgical history)
- Laboratory blood tests (CBC, renal functions, LFT, CK, lipid profile, HIV, hepatitis viral profile and pregnancy test)
- Blood sample processed for ROCK activity assay on peripheral leukocytes, and plasma stored in biobank for future/ancillary biomarker studies.
- Characterization of genotype in cases with multiple lesions, or referral to Angioma Alliance for genotyping through the Alliance's program ([www.angioma.org](http://www.angioma.org)).

### **6.2.2 Second screening visit (V1) – Baseline**

The screening visit (V0) and the baseline visit (V1) could occur on the same day at the investigator's discretion. The following will be performed at the baseline visit prior to each subject receiving study treatment:

- Eligibility criteria (inclusion/exclusion criteria)
- Physical, neurological and mini-mental state examination (MMSE)
- Modified Rankin score (mRS)
- Euro-QoL 5D, Euro-QoL VAS, Neuro-QoL SF Cog evaluations
- MRI
- Discuss results of MRI
- Meeting with Trial Nurse
- Evaluation for suitability of atorvastatin therapy
- Randomization
- Providing study monitoring device (eDiary/smart bottle)

### **6.2.3 Three month phone call and safety labs (V2)**

The 3 month visit (V2) will consist of a phone call from the Trial Nurse or coordinator as well as laboratory tests. During the phone call, the TN or coordinator will collect information about the patient's current mRS, concomitant medications, and any adverse events. The following laboratory tests need to be completed as part of standard care at 3 months:

- Renal function
- LFT
- CK

**6.2.4 Six and 9 month follow-up phone call (V3 and V4)**

The 6 and 9 month visits will consist of a phone call from the Trial Nurse or coordinator to collect the following information:

- Modified Rankin score (mRS)
- Concomitant medications
- Adverse events

**6.2.5 Twelve month follow-up visit (V5) – 12m +/- 4wks**

The following assessments will be performed on all subjects at 12 months from enrollment:

- Laboratory blood tests (Renal functions, LFT, CK and lipid profile)
- MRI with DCEQP and QSM
- mRS
- Euro-QoL 5D, Euro-QoL VAS, Neuro-QoL SF Cog evaluations
- Intervention adherence/ adverse events review: review results of laboratory investigations, review study monitoring device (eDiary/smart bottle), manual pill count, elicit drug-related adverse events, full medical examination, MMSE, assess suitability for continuation of statin therapy.
- Neurosurgical review: neurological examination, MMSE, discuss results of MRI, dose modification if necessary.
- Blood sample processed for ROCK activity assay on peripheral leukocytes, and plasma stored in biobank for future/ancillary biomarker studies.

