### **3.2 Blinding**

The study is designed as a double-blind, placebo-controlled clinical trial. Enrolled subjects will be blinded to treatment rendered, as will the PIs, outcomes assessors processing the radiological biomarkers, the trial staff at the Chicago site and the Data Coordinating Center (DCC) staff at the Baltimore site. Atorvastatin and placebo capsules will be formulated by a third party pharmacy representing two different doses of atorvastatin (40 and 80mg) or placebo. The Research Pharmacy at the Chicago site shall be informed electronically about the treatment allocation (see Section 3.3 Randomization), and it shall dispense the appropriate drug or placebo in a 6-month supply, given at enrollment then mailed by the study team biannually, one month ahead of expected date of exhausting the supply. Subjects in the treatment group will receive unlabeled color coded capsules containing pulverized atorvastatin tablets in the designated doses. Subjects in the control group will receive identical looking color coded capsules containing inactive filler. In the case of dose de-escalation, the Research Pharmacy shall be instructed about the decision to lower the dose, and it shall dispense capsules of different color indicating the lower dose, or identical colored placebo capsules, without breaking the blind to the patient or research team.

The Baltimore statistician shall prepare safety reports including comparison of adverse events (AEs) and interim outcome measures by treatment group labeled as A or B without identifying either as active treatment (See Sections 9.4 on Data Monitoring and 10.3 on Quality Assurance and Data and Safety Monitoring). If a concern is raised about safety and the need to suspend trial enrollment, the independent medical safety monitor (IMSM) may request to identify A or B groups as treatment or placebo. Individual subjects will not be identifiable in the safety reports, maintaining the double-blinding if the trial is resumed.

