**6.2.7 End of study visit (V9) – 24m +/- 4wks**

The following interventions will be performed on all subjects at 24 months from enrollment:

- Laboratory blood tests (renal functions, LFT, CK and lipid profile)
- Intervention adherence/ adverse events review: review results of laboratory investigations, review study monitoring device (eDiary/smart bottle), manual pill count, elicit drug-related adverse events, full medical examination, MMSE, assess suitability for continuation of statin therapy
- MRI with DCEQP and QSM
- mRS
- Euro-QoL 5D, Euro-QoL VAS, Neuro-QoL SF Cog evaluations

- Neurosurgical review: neurological examination, MMSE and discuss results of MRI
- Blood sample processed for ROCK activity assay on peripheral leukocytes, and plasma stored in biobank for future/ancillary biomarker studies.

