### **6.3.6 Laboratory tests**

These assessments will be performed at the baseline, 12 and 24 month follow up visits prior to every MRI scan according to the study schedule (Table 1) (84, 85). Assessments marked with an asterisk (\*) will also be performed at the 3 month follow up visit as part of the subject's local, routine care to assess statin tolerance:

- **Complete blood count (CBC):** performed as part of baseline blood tests and repeated only if clinically indicated
- **Renal functions\*:** Renal functions and electrolytes, performed at screening to determine subjects baseline renal function and safety of IV contrast material. Repeated prior to every scheduled MRI scan and as clinically indicated. Could be substituted with pin-prick tests prior to IV contrast administration according to local protocol.
- **Liver function tests (LFTs)\*:** liver transaminases, alkaline phosphatase and bilirubin performed at baseline and at 6 months from enrollment on all subjects.
- **Thyroid function tests (TFTs):** performed at screening and when investigating adverse events.
- **Serum creatine kinase (CK)\*:** performed at baseline and at 6 months from enrollment on all subjects.
- **Lipid profile:** Total cholesterol, HDL and LDL.
- **Hepatitis viral profile**
- **HIV** (Known cause of myopathy, which is one of the most common side effects of statins resulting in cessation of treatment).
- **Pregnancy test**
- **Blood sample shall also be drawn for ROCK activity assay on peripheral leukocytes** as detailed in 6.4 below, and plasma freeze-stored for future or ancillary biomarker studies.

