## 7. MANAGEMENT OF ADVERSE EXPERIENCES

In the event of an adverse event (Table 2), the first concern will be for the safety of the subject. Subjects will be closely monitored and are required to notify the trial PI or designated TN of any new symptoms that occur following treatment onset. Managed adverse events include all new symptoms, whether expected or unexpected, which are assessed by the TN, in consultation with the on-site statin expert physician, to be reasonably or possibly related to the study intervention. All adverse events that the study team is notified about will trigger at least an unscheduled telephone evaluation. During the evaluation, a member of the study team will assess the seriousness of the reported event, its attributability to the study intervention and advise the subject regarding the treatment plan, including whether to continue on the study drug (99, 100). Serious criteria, definitions, and guidance for reporting follow in section 10.4: Adverse Experience Reporting.

Historically, very low levels of low-density lipoproteins (LDL) have been sporadically associated with some detrimental effects. However, clinical trials on statin therapy have not demonstrated any substantial correlation between lower LDL levels and safety. There is no evidence that lowering low-density lipoprotein levels in people with normal cholesterol profile is inherently unsafe (101).

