## 8. CRITERIA FOR INTERVENTION DISCONTINUATION

Atorvastatin/Placebo administration will be discontinued for any of the following reasons (designated as serious AEs or Category C in the preceding Table 2):

- Symptomatic intracerebral hemorrhage (ICH) whether primary, arising from index cavernous malformation that previously bled, or in other lesion, or other ICH of any kind
- Severe allergic reaction
- Rhabdomyolysis
- Markedly elevated liver enzymes
- Liver failure
- Pancreatitis
- Pregnancy
- Intolerable adverse events that persist or recur after serial dose reduction.
- In the investigator's judgment, withdrawal from the trial would be in the subject's best interest (Drug interaction/glycemic control).
- The subject or legal representative withdraws consent, or patient undergoes surgical resection or irradiation of CCM lesion, other brain surgery or irradiation for any cause.
- Patient develops clinical indications for statin use for cholesterol or cardiovascular indications unrelated to CCM.

If one or more of these events occur after commencing the study drug, the subject will be considered to have reached a safety endpoint. Study drug or placebo shall be discontinued. All subjects reaching safety endpoints will be followed through the 24-month follow up visit as a part of the outcome assessment for the study. An attempt will be made to contact subjects who withdraw from the study or who are lost to follow up for safety evaluation. If these subjects wish not to cooperate there will be no additional follow up.

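### Lipid results at 12 and 24 months go to site staff who are meant to be blinded, giving a strong but imperfect cue to the arm for site-rated secondary and safety outcomes

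*Combined protocol and SAP*

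**What the plan says.** **Sampling.** Section 6.3.6 defines the lipid profile as "Total cholesterol, HDL and LDL" and sets the timing: "These assessments will be performed at the baseline, 12 and 24 month follow up visits prior to every MRI scan according to the study schedule". The same three time points appear in Table 1. Section 6.2.5 lists "Laboratory blood tests (Renal functions, LFT, CK and lipid profile" at 12 months, and Section 6.2.7 lists "Laboratory blood tests (renal functions, LFT, CK and lipid profile" at 24 months. The 3-month tests in Section 6.2.3 do not include lipids.

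**Review.** At 12 months the adherence and adverse-event item tells the site to "review results of laboratory investigations, review study monitoring device", among other tasks. The same item covers MMSE, eliciting drug-related adverse events and judging whether treatment should continue. mRS is rated at the same visit. The 24-month visit has a matching item. Neither sets lipids apart from the other laboratory results.

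**Blinding.** Section 3.2 blinds subjects, the PIs, the assessors who process the imaging biomarkers, "the trial staff at the Chicago site" and the coordinating centre. Section 9.1 adds the clinical personnel. The safeguards described are look-alike capsules, dispensing by the research pharmacy, and reports labelled A and B.

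**Drug effect.** Section 7 considers the safety of "lowering low-density lipoprotein levels in people with normal cholesterol profile". It therefore takes LDL lowering by this drug class as given, but states no size.

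**The concern.** Look-alike capsules protect the blind only if no routine result separates the arms. Here a pharmacodynamic marker of the study drug is measured before and during treatment and handed to the people who go on to rate the subject. A rater who suspects the arm may score function, ask about symptoms or attribute an adverse event differently, without intending to.

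What is at stake is the credibility of the between-arm comparisons on secondary and safety outcomes that depend on site judgment. In a small proof-of-concept trial, these will be read closely next to the imaging result.

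**Working it through.** The plan has no figure of its own to reproduce on this point. The check has three steps.

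**1. Is the before/after contrast readable?** Exclusion 4.2.6 rules out anyone with more than 7 days of statin in a row, or more than 14 days in total, in the 12 months before enrollment. Baseline lipids are therefore essentially off-statin, and each subject serves as their own control at months 12 and 24.

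**2. Who sees the results, and what do they rate?**

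| Outcome | Rater | Exposure |
|---|---|---|
| mRS and adverse events at 3, 6 and 9 months | Trial nurse or coordinator (6.2.3, 6.2.4) | None: no follow-up lipids yet |
| mRS, MMSE and adverse events at 12 months | Site team (6.2.5) | Only if results are back before rating |
| mRS and adverse events at 15, 18 and 21 months | Trial nurse or coordinator (6.2.6) | Yes: 12-month results known |
| mRS, MMSE and adverse events at 24 months | Site team (6.2.7) | Yes: 12-month results known |
| Adverse-event causality | Investigator with the medical safety monitor (10.4.2.1) | Yes, once results are known |
| Lesion diameter, the basis of the 2 mm expansion outcome | PI (6.5.1, 9.2) | Yes, once results are known |
| QSM (primary) | Imaging assessors, listed separately (3.2), on de-identified images (6.5.3) | Not shown |

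Section 7.1 also gives the trial nurse and coordinator access to each subject's eCRF, so any lipid values entered there would be open to them.

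**3. How strong is the cue?** Let d be the mean LDL fall on active drug (none on placebo) and s the SD of within-person percent change. The documents give neither, so I assume d = 30-50% and s = 15-25 points. With 1:1 allocation and a cut at d/2, the proportion guessed correctly is p = Phi(d/(2s)); 0.50 is chance.

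| d | s = 15 | s = 20 | s = 25 |
|---|---|---|---|
| 30% | 0.84 | 0.77 | 0.73 |
| 40% | 0.91 | 0.84 | 0.79 |
| 50% | 0.95 | 0.89 | 0.84 |

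The extremes are Phi(30/50) = Phi(0.60) = 0.73 and Phi(50/30) = Phi(1.67) = 0.95.

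**Allowing for subjects off drug.** Section 9.3.2 expects 20-30% to stop for symptomatic hemorrhage and under 5% to leave for intolerance. Taking 5% as the upper limit, the sum is 25-35%. An active subject off drug looks like placebo and is guessed correctly with probability 1 - p. If a fraction f of the active arm is off drug, the overall proportion is

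(1/2)[p + (1 - f)p + f(1 - p)] = p - f(2p - 1)/2.

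- d = 50, s = 15, f = 0.25: 0.952 - 0.25 x 0.904/2 = 0.84.
- d = 30, s = 20, f = 0.35: 0.773 - 0.35 x 0.546/2 = 0.68.
- d = 30, s = 25, f = 0.35: 0.726 - 0.35 x 0.452/2 = 0.65.

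This adjustment suits month 24 better than month 12, because the expected losses build up over two years.

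**The case against.** **The primary outcome looks protected.** A reader might infer that the QSM result is unblinded too. The documents do not support that. The imaging assessors are listed apart from the trial staff, the images carry only subject number and scan date, and nothing gives the readers laboratory results. Nothing bars access either, and the regions of interest are hand-drawn at the same site. The gap deserves one sentence in the protocol, but it is not a demonstrated fault.

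**The cue is not certain.** A reader might conclude that the site could identify nearly every subject. Under the assumptions above, 5-27% are misclassified even with everyone on drug, and more with stopping. These figures also measure guessing, not bias; no distortion of any outcome estimate has been shown. That objection stands.

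**Some judgments are tied to other criteria.** Dose reduction follows the Category B events in Table 2, which has no lipid criterion. Symptomatic hemorrhage requires imaging and adjudicated criteria. I do not count either as exposed.

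**The Section 8 stop.** One criterion is "Patient develops clinical indications for statin use for cholesterol or cardiovascular indications unrelated to CCM". It is tempting to infer that this would fall mainly on placebo subjects, whose lipids are untreated. That is speculative. Exclusion 4.2.7 removes subjects with an indication at entry, 4.2.18 requires an outside provider who could identify one independently, and subjects who stop are followed and kept in the intention-to-treat analysis. Masking lipids would not remove any such imbalance.

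**Masking may be specified elsewhere.** Section 10.3.2 mentions a Manual of Operations and Procedures that is not among the documents. The fair statement is that no masking appears in this document.

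**Conclusion.** The point holds for secondary and safety outcomes rated by the site: mRS, MMSE, adverse-event elicitation and causality, and lesion size measured by the PI. Followed as written, the plan gives staff who are meant to be blinded a cue well above chance. Exposure is clear from month 15; at month 12 it depends on whether results return before rating; ratings before month 12 are untouched.

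The size is illustrative: 73-95% correct guesses under the assumed LDL fall and SD, and about 65-84% over the same range if 25-35% of the active arm is off drug. It rests on assumed inputs and on lipid results being reviewed with the other laboratory results, which is the plain reading of Sections 6.2.5 and 6.2.7. It does not show that the primary analysis is compromised. It is a worthwhile and inexpensive repair.

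**What to change.** Keep the lipid samples and change who sees the results.

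- Withhold post-randomization lipid results from the PI, trial nurse, coordinator and image readers, and from the eCRF views they can open, until database lock.
- Send the results to a clinician already available to the trial who neither rates outcomes nor adjudicates adverse events, and who contacts the site only when the protocol's existing rules require action. The external statin consultant assists the team that adjudicates adverse events (Sections 9.4.1 and 10.3.2). If that person is used, exclude them from adjudication; otherwise the cue simply moves to an adjudicator.
- State that QSM and DCEQP readers have no access to laboratory results.
- Leave CK, LFT and renal results going to the site as now.

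The cost is a laboratory routing instruction, an eCRF access setting and a few lines of protocol text. Visits, samples and sample size are unchanged. There are two drawbacks: a small delay in clinical use of lipid results, and the chance that any contact from the clinician itself hints at that subject's arm.
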